 - Illness during pregnancy (e.g., virus infection).
 - QUVIVIQ exposure (start/stop date, dosage, frequency, reason for discontinuation, if applicable).
 - Other medication or biological product exposures, including other insomnia medications, prescription drugs, over-the-counter products, supplements (start/stop date, dosage, frequency, indication).
 - Substance use (e.g., tobacco, alcohol, illicit drugs, marijuana, caffeine consumption).
 - Chemicals and environmental hazards (e.g., radiation).
 - AEs that occurred from the date of the LMP to study enrollment: patient AEs and SAEs in Cohort A (following QUVIVIQ exposure) and in the Cohort B including event, start date, ongoing or end date, seriousness, severity, relationship to QUVIVIQ, outcome, hospitalization, duration or hospitalization, and action taken.

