5.6.1.2.1 During pregnancy follow-up (estimated at approximately 14, 21, and 34 weeks gestation)

- Date of contact.
- Reporter of information (e.g., patient, HCP, other).
- Current weight.
- Changes in lifestyle risk factors (e.g., smoking, caffeine, alcohol use, illicit drug use, marijuana use).
- Insomnia information including but not limited to insomnia improvement.
- Changes in comorbid conditions.
- QUVIVIQ treatment: start and stop dates, dose, dosing frequency, reason for discontinuation, if applicable.
- Current medication (including other insomnia treatments, over-the-counter medications, folic acid and other vitamins, herbal remedies or supplements, vaccinations, or other medication use to treat chronic conditions or comorbidities): start and stop dates, dose, dosing frequencies.
- Ultrasound results for gestational dating.
- Prenatal test results.
- Pregnancy outcome: live births, spontaneous abortions, stillbirths, elective or therapeutic terminations, and autopsy results and pathology reports, if available.
- Reason for elective or therapeutic termination: prenatal testing finding, risk to mother's health, or undesired pregnancy.
- Congenital malformations noted: description and attribution.
- Patient AEs and SAEs in Cohort A and in Cohort B: event, start date, ongoing or end date, seriousness, severity, relationship with QUVIVIQ, hospitalizations, duration of hospitalization, outcome, and action taken.

5.6.1.2.2 *At delivery*

- Reporter of information (name and position).
- Pregnancy outcome: live births, spontaneous abortions, stillbirths, elective or therapeutic terminations.
- Reason for elective or therapeutic termination: prenatal testing finding, risk to mother's health, or undesired pregnancy.
- Autopsy results and pathology reports, if available.
- Mode of delivery: vaginal delivery, assisted delivery / cesarean section, type of anesthesia.
- Insomnia information including but not limited to insomnia improvement.

23 October 2023, page 52/90

Doc No D-23.335

Confidential

- Changes in comorbid conditions.
- QUVIVIQ treatment: start and stop dates, dose, dosing frequency, reason for discontinuation, if applicable.
- Current medications (any other insomnia treatments, folic acid and other vitamins, herbal remedies or supplements, vaccinations, or other medications used to treat chronic conditions or comorbidities): start and stop dates.

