5.7.1.3 Primary analysis

The final primary analysis will be conducted once all data collection is complete, including up to 21 months of follow-up for enrolled patients. Only women with prospective pregnancies (i.e., outcome of the pregnancy is not known at time of enrollment) will be included in the primary analysis.

Confidential

The primary outcome for this study is major congenital malformations in infants. All other outcomes will be classified as secondary.

The primary analysis will use risk ratios (one-sided 97.5% CI) to compare major congenital malformations in infants between Cohort A and Cohort B1 among women with first trimester exposure to their respective insomnia medications. Women exposed to QUVIVIQ who take other medications for insomnia at any time during pregnancy will be excluded from the primary analysis. Women with known teratogen exposure during pregnancy will be included in the primary analysis. Sensitivity analyses will be conducted evaluating timing of exposure. Additional sensitivity analyses will be conducted, including women exposed to QUVIVIQ who were exposed to other insomnia medications, and excluding those with known teratogen exposure [Section 5.7.4.4].

Adjudicated major congenital malformations reported up to 1 year of age by the mother or by an HCP will be included in the primary analysis. Pregnant women who receive any prenatal screening after enrollment (post-enrollment) that provides knowledge of the pregnancy outcome will be included in the primary analysis. Decision criteria with regard to prenatal testing before enrollment (pre-enrollment) will be applied to the study population for inclusion in the primary analysis as follows: pregnant women with pre-enrollment prenatal testing who have not received the test results at the time of enrollment will be included in the primary analysis, while pregnant women who had prenatal testing pre-enrollment where the result is known prior to enrollment will be included or excluded from the primary analysis depending on the result of the test (see Table 5 for pertinent descriptions for inclusion in analyses based on timing and the results of prenatal screening tests).

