5.7.4.2 Analysis of primary and secondary endpoints

The prevalence of major and minor congenital malformations will be calculated using the MACDP convention. If needed for future analyses, minor and major congenital malformations will also be calculated using the EUROCAT convention using the same process. Major malformations will be analyzed separately from minor malformations, with the primary analysis including only adjudicated major congenital malformations. The total prevalence will be calculated by dividing the number of women with any adjudicated cases of each event (observed in live births, fetal deaths, elective or therapeutic terminations, and at any gestational age) by the total number of pregnancies (excluding spontaneous terminations and ectopic or molar pregnancies). The prevalence at birth will be calculated as number of cases observed in live births and stillbirths divided by the total number of births (stillbirths + live births). Data analysis for major congenital malformations will be based on exposure to QUVIVIQ from within 5 half-lives prior to conception through the end of the first trimester.

Confidential

The prevalence of pregnancy complications, including preeclampsia, pregnancy-induced hypertension, gestational diabetes, and preterm labor, will be summarized by dividing the number of pregnant women with that complication by the total number of pregnant women.

The prevalence of spontaneous abortions will be calculated by dividing the number of women with fetal loss occurring before 20 weeks gestation by the total number of pregnant women.

The prevalence of elective and therapeutic abortion will be estimated similarly as separate outcomes.

The prevalence of preterm birth will be calculated by dividing the number of cases by the total number of births (stillbirths + live births). The prevalence of small for gestational age will be calculated by dividing the number of cases by the total number of live births.

For other events of interest occurring in developing neonates and infants, including mortality, hospitalizations for serious illness, growth, and developmental delays, the prevalence will be calculated as the number of cases divided by the total number of live births.

The prevalence of primary and secondary outcome measures will be presented with 97.5% CIs for binomial proportion. The analyses summarized in this section will be performed on the Cohort A and Cohort B.

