5.7.4.4 Sensitivity and subgroup analyses

Sensitivity analyses will be performed on both Cohort A and Cohort B if sufficient sample size allows, including but not limited to that which is listed in Table 6.

Table 6 Sensitivity analysis subgroups and outcomes analyzed

Subgroup	Outcome analyzed
Women who have received any prenatal testing that provides knowledge of pregnancy outcome, regardless of findings	Major congenital malformations
Women who have received any prenatal testing that provides knowledge of pregnancy outcome before enrollment, where results are known, regardless of the findings	Major congenital malformations
Women who received any first trimester prenatal screening that provides knowledge of pregnancy outcome before enrollment where result is known to be negative	Major congenital malformations
Women with exposure to QUVIVIQ preconception and in each trimester of exposure ^a	Major congenital malformations
Women with exposure to QUVIVIQ preconception and in each trimester of exposure	Minor congenital malformations
Women with exposure to insomnia medications (Cohorts A and B1) by type (continuous vs intermittent), duration, and dosage of exposure	Major congenital malformations
Women in the primary analysis	Spontaneous abortion occurring before 22 weeks of gestation
Women in primary analysis based on gestational age of enrollment	Spontaneous abortion
Women who did not take known teratogens during pregnancy	Major congenital malformations
Women with clinically confirmed insomnia disorder	Major congenital malformations
Women with exposure to QUVIVIQ and additional medications for insomnia treatment from preconception through end of pregnancy	Major congenital malformations

^a The primary cut point will be the date of conception (LMP + 14 days) to the end of the first trimester (14 weeks gestation), additional sensitivity cut points will include 18 weeks prior to conception through the end of the first trimester, conception date to the end of the pregnancy, 18 weeks prior to conception to the end of pregnancy, second trimester exposure only, and third trimester exposure only.

LMP = last menstrual period.

Full details will be described in the SAP.

Confidential

Subgroup analysis

Both Cohort A and Cohort B (overall and separately for Cohorts B1 and B2) will be summarized and compared for primary and secondary outcomes both overall and by the subgroups of the following parameters, if sufficient sample size allows:

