Appendix 2 List of known teratogens

This list of known teratogens and their half-lives (last updated 1 March 2023) will be used for exclusion purposes in the analysis. This list will be reviewed at the time of analysis to update it with any changes since protocol finalization.

Substance	Half-Life
Acitretin	49 hours
Acenocoumarol	8–11 hours
Afatinib	37 hours
Aflibercept	5–6 days
Alitretinoin	9 hours
Altretamine	4.7–10.2 hours
Azacitidine	41 minutes
Arsenic trioxide	10–14 hours
Ambrisentan	9 hours
Aminopterin ^a	3.6 hours
Amsacrine	8–9 hours
Asparaginase	14.2–44.2 hours
Axitinib	2.5–6.1 hours
Azathioprine	5 hours
Benazepril	10–11 hours
Bendamustine	28.2 minutes
Bevacizumab	18 days
Bexarotene	1–3 hours
Bleomycin	115 minutes
Bortezomib	40–193 hours
Bosutinib	36 hours
Brequinar ^b	11.1–36.6 minutes in initial phase,
	12.5–25.0 hours in terminal phase
Busulfan	2.3–2.5 hours
Bosentan	5 hours
Cabazitaxel	95 hours
Cabozantinib	110 hours
Capecitabine	0.8–0.9 hours
Carboplatin	90 minutes–6 hours
Carmustine	96 hours
Cetuximab	70–100 hours

QUVIVIQ® (daridorexant) Insomnia disorder ID-078A403 Version 4

23 October	2023,	page	82/90
------------	-------	------	-------

Substance	Half-Life
Chlorambucil	1.8 h
Chlortetracycline	5.6 h
Cisplatin	25–49 min
Cladribine	1 day
Clofarabine	5.2 h
Ceritinib	31–41 h
Clomiphene	5–7 days
Clorazepate	2 days
Cytarabine	10 min
Captopril	< 3 h
Carbamazepine	35 h
Cyclophosphamide	3–12 h
Danazol	9–23.7 h
Demeclocycline	10–16 h
Doxycycline	18–22 h
Dutasteride	5 weeks
Dabrafenib	10 h
Dacarbazine	2.9–75 min
Dactinomycin	36 h
Dasatinib	5-6 h
Daunorubicin	45 min in initial phase, 18.5 h in terminal phase
Didanosine	30 min
Diethylstilbestrol ^c	2–3 days
Divalproex	13–19 h
Docetaxel	4 min–11 h pending phase
Dolutegravir	14 h
Doxorubicin	12 min–30 h pending phase
Enalapril	14 h
Enalaprilat	11 h
Enzalutamide	5.8 days
Ethosuximide	17–56 h
Epirubicin	40 h
Erlotinib	36.2 h
Estramustine	20 h
Ethotoin	3–9 h

QUVIVIQ® (daridorexant) Insomnia disorder ID-078A403 Version 4 23 October 2023, page 83/90

Substance	Half-Life
Etoposide	0.6–2 h
Etretinate	49 h
Eribulin	40 h
Everolimus	30 h
Finasteride	4.5 h
Fluconazole (chronic, high-dose only)	20–50 h
Fosinopril sodium	12 h
Fosphenytoin sodium	15 min
Fenprocoumon	5–6 days
Floxuridine ^e	10–20 min
Fluorouracil	10–20 min
Gefitinib	48 h
Gemcitabine	19.4 h
Hydroxycarbamide	12 h
Hydroxyurea	12 h
Ibrutinib	4–6 h
Idarubicin	15 h
Ifosfamide	15 h
Imatinib	18 – 40 h
Isotretinoin	18 h
I-131	8 days
Irinotecan	6–12 h

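### The teratogen-free sensitivity analysis in Table 6 has no exemption for listed drugs, such as misoprostol, given to end the pregnancy or induce labour, so it can drop malformation cases because of how the pregnancy ended

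*Protocol*

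**What the plan says.** Appendix 2 gives the teratogen list an analytic role: "This list of known teratogens and their half-lives (last updated 1 March 2023) will be used for exclusion purposes in the analysis". Misoprostol is on it with a half-life of 20–40 minutes and no restriction on timing, dose or purpose. The list does carry restrictions elsewhere: one entry reads "Fluconazole (chronic, high-dose only", and tretinoin is limited to the oral form.

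Table 6 in Section 5.7.4.4 uses the list to define a sensitivity set for major congenital malformations: "Women who did not take known teratogens during pregnancy". Section 5.7.1.3 announces the same analysis and says of the main one: "Women with known teratogen exposure during pregnancy will be included in the primary analysis".

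Section 5.7.4.2 counts malformation cases in total prevalence when they are "observed in live births, fetal deaths, elective or therapeutic terminations, and at any gestational age". Follow-up under Section 5.6.1.2.1 foresees termination after an abnormal finding: "Reason for elective or therapeutic termination: prenatal testing finding, risk to mother's health, or undesired pregnancy".

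**The concern.** A restriction to women without teratogen exposure should remove pregnancies in which another drug could have caused the malformation. A drug given to end a pregnancy or start labour is different: its use follows from the course of the pregnancy and cannot explain a malformation already found. If such use counts as exposure, membership of the analysis set depends partly on the outcome.

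Terminations after a finding are foreseeable in this registry. Section 5.7.1.3 and Table 5 keep women whose prenatal testing comes after enrolment, and also women with known abnormal results that are unrelated to aneuploid or genetic disorders. A malformed pregnancy ended with a listed drug is then a case in the primary analysis and absent from the teratogen-free one. A difference between the two results could not be read as the effect of removing teratogens, which is the purpose of the sensitivity analysis.

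**Working it through.** **Expected cases.** The plan's formula (Section 5.5.1) with P_A = 3.15%, P_B1 = 3%, margin 6% and r = 2 gives

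N_A = 3 × (0.8416 + 1.9600)² × [(0.0315 × 0.9685 + 0.03 × 0.97)/2] / [2 × (0.0015 − 0.06)²] = 102.5,

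which agrees with the stated 102 (and 204 in B1) to rounding. Expected cases are 102 × 0.0315 = 3.2 in A and 204 × 0.03 = 6.1 in B1. One case lost in A is worth 1/102 = 1.0 percentage point.

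**Equal losses.** Suppose a share f of cases leaves in both cohorts and no non-cases leave (f is assumed; the protocol gives none):
- f = 10%: 2.9 and 5.5 cases remain.
- f = 30%: 2.2 and 4.3 remain. Prevalences are 2.25/101.0 = 2.23% and 4.28/202.2 = 2.12%, ratio 1.05.
- f = 50%: 1.6 and 3.1 remain.

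The ratio stays at its planned 3.15/3.00 = 1.05. Only the number of cases and the prevalence fall.

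**Range of losses.** Table 4 gives 62% live births, 18% terminations and 1.4% fetal deaths or stillbirths, so 81.4 per 100 pregnancies enter the total-prevalence denominator. Let t be the share of malformed pregnancies terminated, m the share of terminations using a listed drug, and i the share of births using one. All three are assumptions.
- Cases removed = t·m + (1 − t)·i
- Pregnancies removed = (18·m + 63.4·i)/81.4

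Low end (t = 0.2, m = 0.3, i = 0.05): cases 0.06 + 0.04 = 10%; pregnancies 8.57/81.4 = 10.5%.

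High end (t = 0.5, m = 0.8, i = 0.25): cases 0.40 + 0.125 = 52.5%; pregnancies 30.25/81.4 = 37%.

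If t equals the background 18/81.4 = 22%, the two losses are identical and prevalence does not change.

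**Unequal losses.** Take m = 0.6 and i = 0.1, with equal overall termination rates so that the denominators cancel. If t = 0.50 in A and 0.25 in B1, the cases kept are 1 − (0.30 + 0.05) = 0.65 and 1 − (0.15 + 0.075) = 0.775. The observed ratio is the true one times 0.65/0.775 = 0.84, so a true 2.0 reads as 1.68. If the two values of t are swapped, the factor is 0.775/0.65 = 1.19. The shift comes wholly from the assumed cohort difference and can go either way.

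**The case against.** **Reach.** A reader might infer that the registry's non-inferiority conclusion is biased. The documents do not support that. Section 5.7.1.3 keeps these women in the primary analysis, and the affected row is one of several sensitivity analyses that run only if numbers permit. This stands.

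**Left to the SAP.** Section 5.7.4.4 defers full details of Table 6, and Appendix 2 is to be reviewed at the time of analysis. This stands only in part. The protocol states the rule as any use during pregnancy, so an exemption would depart from the text rather than complete it. The list review is described as an update for changes since finalization, and exemptions chosen then would be chosen with outcomes in hand.

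**Mechanism.** Section 5.7.4.2 already leaves spontaneous terminations out of the total-prevalence denominator, so managing a loss before 20 weeks removes no one from it. Terminations do not enter the separate prevalence at birth at all. Both points stand and narrow the problem to total prevalence, with later fetal deaths and induced births as secondary routes.

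**Recording.** Baseline capture is broad: "Other medication or biological product exposures, including other insomnia medications, prescription drugs, over-the-counter products, supplements (start/stop date, dosage, frequency, indication". A drug given to end an enrolled pregnancy comes after baseline, however. The later lists in Sections 5.6.1.2.1 and 5.6.1.2.2 name mainly insomnia treatments, supplements, vaccinations and chronic-condition medicines, and do not list indication. If the use goes unrecorded, no one is removed. This stands, and it is why the number affected is unknown.

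**A first-trimester cut-off.** Because the main malformation analysis rests on "exposure to QUVIVIQ from within 5 half-lives prior to conception through the end of the first trimester", a reader might infer that the teratogen window must also close there. The documents do not require it. Section 5.7.1.3 and the Table 6 footnote plan malformation analyses for later exposure, and a cut-off at 13+6 weeks would not spare first-trimester terminations.

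**Conclusion.** The point holds for one sensitivity analysis. As written, the exclusion can remove a malformation case because of how the pregnancy ended. This rests on two things the protocol does not supply: that listed drugs such as misoprostol are used to end or induce pregnancies (general clinical knowledge), and that such use is recorded after baseline.

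The direction and size of any bias are unknown. Equal losses leave the risk ratio unchanged but reduce about 3 and 6 expected cases to fewer still. A shift needs the cohorts to differ in termination or drug use. A reader might take 0.84, or a true 2.0 read as 1.68, as the expected bias towards non-inferiority. The documents give no basis for the 50% versus 25% difference behind those figures, and the reverse difference gives 1.19. This is a minor definitional defect, worth correcting because the correction is cheap and the analysis otherwise cannot be interpreted cleanly.

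**What to change.** Add to the Table 6 row and to Appendix 2: for this analysis, a listed drug given to end the pregnancy, manage a fetal death or induce labour does not count as teratogen exposure. Identify such use by the recorded indication or, where that is missing, by the medication start date relative to the recorded end of the pregnancy. Neither a gestational-age cut-off nor a fixed number of days is needed. Carry the same definition into the SAP before outcomes are reviewed.

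The cost is mainly wording. Medication start and stop dates are already listed at the pregnancy and delivery contacts. The sponsor should confirm that the eCRF gives a date, or a gestational age precise enough to derive one, for the end of terminated pregnancies. The downside is small: some uses may have to be classified from dates alone. The change is to an analysis definition and does not touch clinical care.

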Appendix 3 List of approved non-ORA medications to treat insomnia

This list of known, approved non-ORA medications to treat insomnia or sleep disorders is based the information as of 26 June 2023. This list will be reviewed at the time of analysis to update it with any changes since protocol finalization.

Medication name	Half-life ^a	Medication	Known
		availability	teratogen
Alprazolam	10.7–15.8 h	Prescription	No
Amobarbital	16-40 h	Prescription	No
Butabarbital	100 h	Prescription	No
Brotizolam	14.9 min	Prescription	No
Buspirone	2–3 h	Prescription	No
Chloral hydrate	4–12 h	Prescription	No
Chlordiazepoxide	6–30 h	Prescription	No
Cinolazepam	9 h	Prescription	No
Clomethiazole ^b	3.5–5 h	Prescription	No
Cloral betanine	4–12 h	Prescription	No
Diazepam	48 h	Prescription	No
Diphenhydramine	2.4–9.3 h	Over-the-counter	No
Doxepin	15.3 h	Prescription	No
Doxylamine	10 h	Over-the-counter	No
Estazolam	10–24 h	Prescription	No
Eszopiclone	6 h	Prescription	No
Etizolam	3.4–6 h	Prescription	No
Flunitrazepam	72 h	Prescription	No
Flurazepam	3.1 h	Prescription	No
Loprazolam	12 h	Prescription	No
Lorazepam	14 h	Prescription	No
Lormetazepam	13.6 h	Prescription	No
Melatonin	45 min	Over-the-counter	No
Nitrazepam	24 h	Prescription	No
Oxazepam	6–20 h	Prescription	No
Pentobarbital	15-50 h	Prescription	No
Phenobarbital	53–118 h	Prescription	No
Pregabalin	6.3 h	Prescription	No
Promethazine	9–16 h	Prescription	No
Quazepam	30 min	Prescription	No
Ramelteon	2.6 h	Prescription	No

23 October 2023, page 88/90

Doc No D-23.335

Confidential

Medication name	Half-life ^a	Medication availability	Known teratogen
Ramelteon	1–2.6 h	Prescription	No
Secobarbital ^c	28.9 h	Prescription	No
Tasimelteon	1.3 h	Prescription	No
Triazolam	0.4–18.4 h	Prescription	No
Temazepam	1.5–5.5 h	Prescription	No
Zaleplon	1 h	Prescription	No
Zolpidem	2.5–2.6 h	Prescription	No
Zopiclone	6 h	Prescription	No

Note: This list was generated from the US FDA list of known sleep disorder medications [FDA 2019b], the UK list of sleeping pills and minor tranquilizers [Mind.org], the DrugBank Online database [go.drugbank.com], and the Canadian Drug Summary: Sedatives list [CCSA 2022]. The list was then crosschecked for known teratogenicity against the teratogens provided in Appendix 2. Medications withdrawn at time of protocol approval: Butabarbital and Estazolam

FDA = Food and Drug Administration; UK = United Kingdom; US = United States.

^a Unless otherwise noted, product half-life was extracted from Accessdata.fda.gov [FDA 2022], https://products.mhra.gov.uk/ [products.mhra.gov.uk/], and the DrugBank Online database [go.drugbank.com].

^b Source data: [Jostell 1978].

^c Source data: [Clifford 1974].

